7.7.7. Reporting Periods for Adverse Events, and Serious Adverse Events

The safety reporting period for all AEs, and SAEs is from study Day 1 (predose) through the EOT visit or 30 days after the last study treatment, whichever is later. However, all study protocol-related AEs are to be recorded from the time of informed consent. All SAEs that occur after the safety reporting period and are considered study treatment-related in the opinion of the investigator should also be reported to the sponsor.

SAEs will be followed until significant changes return to baseline, the event stabilizes (recovering/resolving) or is no longer considered clinically significant by the investigator, or the subject dies or withdraws consent. All nonserious AEs will be followed through the safety reporting period. Certain nonserious AEs of interest may be followed until resolution, return to baseline, or study closure.

7.7.8. Serious Adverse Events Require Immediate Reporting

Within 24 hours of observing or learning of an SAE, investigators are to report the event to the sponsor, regardless of the relationship of the event to the study treatment regimen.

For initial SAE reports, available case details are to be recorded on an SAE form. At a minimum, the following should be included:

- Subject number
- Date of event onset
- Description of the event
- Study treatment, if known
- Investigator causality assessment

The completed SAE form and SAE Fax Cover Sheet are to be emailed or faxed to the sponsor's Drug Safety Department within 24 hours (see email or fax number specified on the SAE report form) unless otherwise instructed on the sponsor's SAE form.

Relevant follow-up information is to be submitted to the sponsor as soon as it becomes available.

7.7.9. Sponsor Safety Reporting to Regulatory Authorities

Investigators are required to report all SAEs to the sponsor (see Section [7.7.8](#)).

The sponsor will report all SAEs, including suspected unexpected serious adverse reactions (SUSARs) to regulatory authorities as required per local regulatory reporting requirements.

7.7.10. Vital Signs

Vital signs measures are to include heart rate, blood pressure, and temperature. There is a 5-minute window to perform vital sign collection at the timepoints identified in Section [6](#).

7.7.11. Clinical Laboratory Tests

Samples will be drawn for central and local labs. Local laboratory testing will include institutional standard tests for evaluating safety and making clinical decisions. The following

laboratory assessments will be performed by the local lab to evaluate safety at scheduled time points (see [Appendix A](#)) during the course of the study:

- The chemistry panel is to include the following tests: albumin, alkaline phosphatase, ALT, AST, blood urea nitrogen, calcium, creatinine, chloride, lactate dehydrogenase, phosphorus, potassium, sodium, glucose, total bilirubin, and uric acid.
- The CBC with differential is to include the following tests: white blood cell count with 5-part differential (neutrophils, lymphocytes, monocytes, eosinophils, and basophils), platelet count, hemoglobin, and hematocrit.
- The eGFR should be calculated using the MDRD equation as applicable, with serum creatinine (Scr) reported in mg/dL.

$$\text{GFR (mL/min/1.73 m}^2\text{)} = 175 \times (\text{Scr})^{-1.154} \times (\text{Age})^{-0.203} \times (0.742 \text{ if female}) \times (1.212 \text{ if African American})$$

- Urinalysis
 - Standard urinalysis (Note: specify ± reflexive microscopy)
 - Urine protein and urine creatinine for UPCR via spot urine test
- A serum or urine β -hCG pregnancy test for subjects of childbearing potential
- PT, PTT, INR
- Serology will include assessments of Hepatitis B and C status. If hepatitis C serology is positive, HCV RNA test by PCR is required to confirm.

7.7.12. Physical Examination

Physical examinations should include assessments of the following body parts/systems: abdomen, extremities, head, heart, lungs, neck, and neurological. Measurements of height obtained within the prior 12 months may be utilized.

7.7.13. Pregnancy Testing

For subjects of childbearing potential, a serum or urine β -hCG pregnancy test with sensitivity of at least 25 mIU/mL will be performed at baseline, within 7 days prior to Day 1 of each treatment cycle, and at the EOT visit in Parts A, B, and C. In Part D (containing pomalidomide), a pregnancy test will be performed 10 to 14 days prior to planned Cycle 1 Day 1, within 24 hours prior to planned Cycle 1 Day 1, q2wk during study treatment (prior to Day 1 and Day 15 dosing), and at the EOT visit. A negative pregnancy result is required before the subject may receive study drug. Pregnancy tests may also be repeated as requested per institutional review board/independent ethics committee (IRB/IEC) or if required by local regulations.

7.7.14. Electrocardiograms

Subjects will be monitored for changes in cardiac repolarization through assessment of ECGs conducted in triplicate at times outlined in [Appendix A](#) and Section 6. There is a 30-minute window to perform ECGs. Waiting periods between replicate ECGs are not required.

7.7.15. ECOG Performance Status

ECOG performance status ([Appendix D](#)) will be evaluated at protocol-specific time points defined in [Appendix A](#) and Section 6.

7.8. Appropriateness of Measurements

The safety measures that will be used in this trial are considered standard procedures for evaluating the potential adverse effects of study medications.

Response will be assessed according to 2016 IMWG, which are standardized criteria for evaluating response in MM ([Kumar 2016](#)). The intervals of evaluation in this protocol are considered appropriate for disease management.

Immunogenicity is commonly assessed for biologics; therefore, standard tests will be performed to detect the possible presence of specific antibodies to SEA-BCMA. PK assessments are also common in clinical studies to help characterize dose-exposure-response relationships.

8. DATA QUALITY CONTROL AND QUALITY ASSURANCE

8.1. Site Training and Monitoring Procedures

A study manual with instructions for study compliance and CRF completion will be provided. Prior to the enrollment of subjects at the site, Seagen or its designated clinical and medical personnel will review the following items with the investigator and clinic staff:

- The protocol, study objectives, eligibility requirements, study procedures, registration and withdrawal processes
- Current IB/package insert
- Recording and reporting AEs and SAEs
- Enrollment goals and study timelines
- The CRF completion process and source documentation requirements
- Monitoring requirements
- IRB/IEC review and approval process
- Informed consent process
- Good clinical practice guidelines and related regulatory documentation requirements
- Key study team roles and responsibilities
- Investigational product storage, accountability, labeling, dispensing and record keeping
- Subject coding and randomization (if applicable)
- Study samples/specimen collection, handling and shipping
- Protocol compliance
- Clinical study record keeping, document retention, and administrative requirements

Monitoring visits will occur periodically, with frequency dependent on the rate of enrollment and workload at each site. During monitoring visits, the Seagen representative will typically review regulatory documentation, CRFs, source documentation, and investigational product storage, preparation, and accountability. The CRFs will be reviewed for completeness, adherence to the provided guidelines, and accuracy compared to the source documents. The investigators must ensure that the monitor is allowed to inspect all source documents pertinent to study subjects and must cooperate with the monitor to ensure that any problems noted in the course of the trial are resolved. The investigator must maintain a comprehensive and centralized filing system of all study-related documentation that is suitable for inspection by Seagen or its designated monitors and by quality assurance auditors, or representatives of regulatory authorities.

8.2. Data Management Procedures

Seagen will provide CRF Completion Guidelines for eCRF data entry. Study specific data management procedures will be maintained in the data management plan. Queries resulting from edit checks and/or data verification procedures will be posted electronically in the eCRF.

8.3. Access to Source Data

The investigator will permit the sponsor's representatives to monitor the study as frequently as the sponsor deems necessary to determine that protocol adherence and data recording are

satisfactory. Appropriate measures to protect subject confidentiality are to be employed during monitoring. The CRFs and related source documents will typically be reviewed in detail by the monitor at each site visit. Original source documents or certified copies are needed for review. This review includes inspection of data acquired as a requirement for participation in this study and other medical records as required to confirm that the information contained in the CRFs, such as disease assessments, AEs, and concomitant medications, is complete and correct. Other study records, such as correspondence with the sponsor or its designee and the IRB/IEC and screening and drug accountability logs will also be inspected. All source data and study records must also be available for inspection by representatives of regulatory authorities and the IRB/IEC.

8.4. Accuracy and Reliability of Data

Steps to be taken to assure the accuracy and reliability of data include:

- The selection of qualified investigators and appropriate study centers.
- Review of protocol procedures with the investigators and associated personnel prior to the study.
- Periodic monitoring visits by the designated monitor(s).
- CRFs will be reviewed for accuracy and completeness during monitoring visits to the study centers and/or by centralized monitoring. Any discrepancies will be resolved with the investigator or designees as appropriate.

8.5. Quality Assurance Procedures

The Research and Development Quality group or its designee may conduct audits at the clinical site or other study-related facilities and organizations. Audit reports will be retained by the Research and Development Quality group of Seagen as part of the written record.

8.6. Data Handling and Record Keeping

8.6.1. Data Handling

It is the investigator's responsibility to ensure the accuracy, completeness, legibility, and timeliness of the data reported to the sponsor in the CRFs and in all required reports. Data reported on the CRF that is derived from source documents should be consistent with the source documents or the discrepancies should be explained.

Any change or correction to a CRF will be maintained in an audit trail within the electronic data capture system. Data changes may only be made by those individuals so authorized. The investigator should retain records of the changes and corrections, written and/or electronic.

8.6.2. Investigator Record Retention

The investigator shall retain study drug disposition records and all source documentation (such as original ECG tracings, laboratory reports, inpatient or office patient records) for the maximum period required by the country and institution in which the study will be conducted, or for the period specified by Seagen, whichever is longer. The investigator must contact Seagen prior to

destroying any records associated with the study. If the investigator withdraws from the study (due to relocation, retirement, etc.), the records shall be transferred to a mutually agreed upon designee, such as another investigator or IRB/IEC. Notice of such transfer will be provided in writing to Seagen.

9. DATA ANALYSIS METHODS

9.1. Determination of Sample Size

Up to approximately 131 subjects are expected to be enrolled in this study. This number is based on the following assumptions:

- Up to approximately 45 subjects will be evaluated in Part A (monotherapy dose-escalation and expansion; q2wk dosing).

With the mTPI study design, the exact number of subjects needed to complete the dose-escalation portion of the phase 1 study is unknown because it depends on the number of cohorts required to reach MTD and the number of subjects enrolled in each cohort. This number is based on the assumption that approximately 25 subjects will be evaluated in dose-escalation and that approximately 20 subjects will be evaluated in an expansion cohort at the MTD or optimal dose to further define the safety and antitumor activity of SEA-BCMA.

Operating characteristics of the dose-escalation part of the study, including the average number of subjects allocated to each dose across a variety of toxicity scenarios are presented in the simulation report ([Appendix C](#)).

- Up to approximately 20 subjects will be evaluated in Part B, up to 60 subjects will be evaluated in Part C (up to 20 subjects in Cohort 1; up to 20 subjects in each dose level in Cohort 2) and up to 6 subjects will be evaluated in Part D.

No formal hypothesis is planned. The sample size is selected by providing a reasonable estimation precision. Assuming the observed ORR is between 30 to 70%, the 95% binomial exact CIs are summarized below.

ORR	95% CI (N=20)
30%	12%, 54%
40%	19%, 64%
50%	27%, 73%
60%	36%, 81%
70%	46%, 88%

9.2. Study Endpoint Definitions

Study endpoints are presented in Section [2](#). Endpoint definitions are presented in this section.

9.2.1. Objective Response Rate

A subject is determined to have an OR if, based on the 2016 IMWG uniform response criteria, they achieve a sCR, CR, VGPR, or a PR. The ORR is defined as the proportion of subjects with an OR per investigator. Subjects whose disease response cannot be evaluated per the 2016 IMWG uniform response criteria will be scored as Not Evaluable for calculating the ORR. Subjects who do not have postbaseline response assessment, or the response is Not Evaluable per IMWG criteria will be counted as non-responders in calculation of ORR.

9.2.2. Complete Response Rate

A subject is determined to have a CR if, based on the 2016 IMWG uniform response criteria they achieve a sCR or CR. The CR rate is defined as the proportion of subjects with a CR per investigator. Subjects whose disease response cannot be evaluated per the IMWG uniform response criteria will be scored as Not Evaluable for calculating the CR rate.

9.2.3. Duration of Objective Response

Duration of OR is defined as the time from first documentation of OR (sCR, CR, VGPR, or PR) to the first documentation of disease progression or to death due to any cause, whichever comes first. Disease progression includes objective evidence of tumor progression (based on serum, urine, or BM assessments) and/or clinical progression per investigator. Duration of response will be censored on the date of the last disease assessment documenting absence of PD for subjects who do not have disease progression and are still on study at the time of an analysis, or are removed from study prior to documentation of tumor progression. Subjects who have started a new antitumor treatment prior to documentation of PD will be censored at the last disease assessment prior to start of new treatment.

Duration of response will only be calculated for the subgroup of subjects achieving a sCR, or CR.

9.2.4. Duration of Complete Response

Duration of CR is defined as the time from first documentation of complete response (sCR, CR) to the first documentation of disease progression or to death due to any cause, whichever comes first. Disease progression includes objective evidence of tumor progression (based on serum, urine or BM assessments) and/or clinical progression per investigator. Duration of CR will be censored on the date of the last disease assessment documenting absence of PD for subjects who do not have disease progression and are still on study at the time of an analysis, or are removed from study prior to documentation of tumor progression. Subjects who have started a new antitumor treatment prior to documentation of PD will be censored at the last disease assessment prior to start of new treatment.

Duration of CR will only be calculated for the subgroup of subjects achieving a sCR or CR.

9.2.5. Progression-free Survival

PFS is defined as the time from the start of any study treatment to first documentation of disease progression or to death due to any cause, whichever comes first. Disease progression includes objective evidence of tumor progression (based on serum, urine or BM assessments) and/or clinical progression per investigator. PFS will be censored on the date of the last disease assessment documenting absence of PD for subjects who do not have disease progression and are still on study at the time of an analysis, or discontinuation of study prior to documentation of tumor progression. Subjects who have started a new antitumor treatment prior to documentation of PD will be censored at the last disease assessment prior to start of new treatment. Subjects lacking an evaluation of tumor response after their first dose will have their event time censored

at 1 day. A detailed censoring scheme will be described in the statistical analysis plan (SAP) for the study.

9.2.6. Overall Survival

OS is defined as the time from the start of any study treatment to the date of death due to any cause. Specifically,

$$\text{OS} = \text{date of death} - \text{date of first dose of any study treatment} + 1.$$

OS for subjects who are alive at their date of last contact, including those lost to follow-up, will be censored at the date of last contact. If the last recorded date where a subject is known to be alive is the date of first dose of any study treatment, survival time will be censored on the date of first dose of any study treatment (ie, OS duration of 1 day).

9.2.7. MRD-negativity rate

The rate of MRD negativity will be reported among subjects who achieved VGPR or better.

9.3. Statistical and Analytical Plans

The statistical and analytical plans presented below summarize the more complete plans to be detailed in the SAP. A change to the data analysis methods described in the protocol will require a protocol amendment only if it alters site conduct (eg, adding baseline assessments to define a subgroup). The SAP will be finalized prior to database lock. Any changes to the methods described in the final SAP will be described and justified in the clinical study report.

9.3.1. General Considerations

This is a phase 1 dose-escalation study with subsequent expansion cohort and combination cohort. All analyses will be descriptive.

Descriptive statistics (mean, median, standard deviation, minimum, maximum) will be used to describe continuous variables. Frequencies and percentages will be used to describe categorical variables.

9.3.1.1. Randomization and Blinding

This is a phase 1 dose-escalation and expansion, nonrandomized study. Blinding will not be performed.

9.3.1.2. Adjustments for Covariates

Adjustments for covariates are not planned.

9.3.1.3. Handling of Dropouts and Missing Data

Missing data will not be imputed, with the exception of AE dates while calculating duration of events and treatment-emergent status; details will be provided in the SAP. For time-related endpoints, eg, PFS, subjects who have no specified event will be censored at the time of the last valid assessment of the endpoint(s).

9.3.1.4. Multicenter Studies

There are multiple centers in this study; however, it is not anticipated that any center will accrue enough subjects to warrant an analysis by center.

9.3.1.5. Multiple Comparisons and Multiplicity

No multiple comparisons are planned, and no alpha adjustment is needed in this phase 1 study.

9.3.1.6. Data Transformations and Derivations

Time variables based on 2 dates (eg, start date and end date) will be calculated as (end date - start date +1 [in days]) unless otherwise specified in the planned analysis section.

Baseline values used in all statistical analyses will be the most recent non-missing measurement prior to the first dose of SEA-BCMA unless otherwise specified in the analysis plan.

9.3.1.7. Analysis Sets

9.3.1.7.1. All Treated Subjects Analysis Set

The All Treated Subjects set includes all subjects who receive any amount of SEA-BCMA. The All Treated Subjects set will be used for presentation of safety data and efficacy endpoints.

9.3.1.7.2. Efficacy-Evaluable Analysis Set

The efficacy-evaluable analysis set includes all treated subjects who had both a baseline and at least 1 postbaseline disease assessment per IMWG uniform response criteria, or per investigator claim of clinical progression.

9.3.1.7.3. DLT-Evaluable Analysis Set

The DE Analysis Set includes All Treated Subjects who either experienced a DLT, or were followed for the full DLT evaluation period and received a minimum 75% of the intended total Cycle 1 SEA-BCMA dose, and did not receive prohibited treatment (see Section 5.6.2 and Section 5.6.3). The DE analysis set will be used for determination of the MTD.

Additional details of analyses and analysis sets of subjects may be defined in the SAP.

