Safety assessments will include the surveillance and recording of AEs, including serious adverse events (SAEs); recording of concomitant medications; and measurements of protocol-specified physical examination findings and laboratory tests. Safety will be monitored over the course of the study by the SMC.

Statistical Methods

For SEA-BCMA monotherapy in Part A, dose-escalation and identification of MTD will be guided by the mTPI method. The dose-limiting toxicity (DLT)-evaluable (DE) analysis set includes all treated subjects who either experienced a DLT or were followed for the full DLT evaluation period and did not receive prohibited treatment. The DE analysis set will be used for determination of the MTD. Safety and efficacy endpoints will be summarized with descriptive statistics. The All-Treated Subjects analysis set will include all subjects treated with any amount of SEA-BCMA. The efficacy-evaluable analysis set includes all treated subjects who had both a baseline and at least 1 evaluable postbaseline disease assessment according to the IMWG uniform response criteria ([Kumar 2016](#)), or per investigator claim of clinical progression.

Binomial exact 95% confidence intervals (CIs) for objective response rate (ORR) will be provided.

Assuming the observed ORR is between 30 to 70%, the 95% binomial exact CIs are summarized below.

ORR	95% CI (N=20)
30%	12%, 54%
40%	19%, 64%
50%	27%, 73%
60%	36%, 81%
70%	46%, 88%

Any expansion cohort may also be discontinued at any point at the discretion of the sponsor.

TABLE OF CONTENTS

PROTOCOL SYNOPSIS	2
LIST OF ABBREVIATIONS AND DEFINITIONS OF TERMS	11
1. INTRODUCTION.....	14
1.1. Multiple Myeloma	14
1.2. BCMA	15
1.3. SEA-BCMA.....	15
1.4. Summary of Nonclinical Toxicology.....	15
1.5. Summary of Preclinical Activity	16
1.6. Rationale for Study	16
1.6.1. Rationale for Study Design.....	17
1.6.2. Rationale for Intensive Dosing Schedule (Part B)	17
1.6.3. Rationale for Combination Therapy	18
1.6.3.1. Rationale for Dexamethasone Combination Therapy (Part C).....	18
1.6.3.2. Rationale for Pomalidomide and Dexamethasone Combination Therapy (Part D)..	18
1.6.3.3. Patient Input Into Design.....	18
1.6.4. Benefit-Risk Assessment	18
1.6.4.1. Risk Assessment	18
1.6.4.2. Benefit Assessment.....	18
1.6.4.3. Overall Benefit-Risk Assessment	19
2. OBJECTIVES	20
3. INVESTIGATIONAL PLAN	22
3.1. Summary of Study Design.....	22
3.1.1. Part A: Monotherapy Dose-escalation and Expansion	22

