3.1.3.3. Part D: Pomalidomide and Dexamethasone Combination Therapy Cohort

Enrollment into the pomalidomide/dexamethasone combination therapy cohort may be initiated upon identification of tolerable SEA-BCMA monotherapy doses and schedules as determined by the SMC. Part D will be conducted in the US only.

- In Cohort 1
 - SEA-BCMA will be administered at 1600 mg (the recommended monotherapy expansion dose) on Day 1 and Day 15 of each 28-day cycle (standard dosing).
 - Dexamethasone will be administered on Day 1, Day 8, Day 15, and Day 22 of each 28-day cycle.
 - Pomalidomide will be administered on Days 1 to 21 of each of each 28-day cycle.

DLTs will be evaluated in 6 subjects enrolled at the 1600 mg dose level. The dose will be considered tolerable if ≤ 1 DLT is observed among the first 6 subjects. Further expansion in Part D will be contingent upon review of the data from the 6 subjects in Cohort 1 and a protocol amendment.

Subjects who are deemed not evaluable for DLT during dose finding will be replaced.

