4.4.1. Discontinuation of Study Treatment

A subject's study treatment may be discontinued for any of the following reasons:

- PD
- AE
- Pregnancy
- Investigator decision
- Subject decision, non-AE
- Study termination by sponsor
- Other, non-AE

In Parts A and B (monotherapy), subjects who discontinue SEA-BCMA will be considered discontinued from study treatment. Subjects who discontinue from study treatment will remain on study for follow-up until withdrawal of consent, death, or study closure, whichever occurs first.

In Part C, subjects who discontinue SEA-BCMA and dexamethasone will be considered discontinued from study treatment. Subjects receiving dexamethasone who discontinue corticosteroid therapy may continue to receive SEA-BCMA as monotherapy with medical monitor approval. Subjects who discontinue SEA-BCMA will be considered discontinued from study treatment.

In Part D, subjects who discontinue SEA-BCMA, dexamethasone, and pomalidomide will be considered discontinued from study treatment. Subjects receiving dexamethasone who discontinue corticosteroid therapy may continue to receive SEA-BCMA and pomalidomide with medical monitor approval. Subjects who discontinue pomalidomide may continue to receive SEA-BCMA and dexamethasone with medical monitor approval. Subjects who discontinue SEA-BCMA will be considered discontinued from study treatment.

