5.4.4. Dose Modifications

Suggested dose modifications and supportive care by toxicity are listed in [Table 7](#).

Table 7: Recommended dose modifications for pomalidomide-related toxicity

NCI-CTCAE Category	Toxicity	Recommended Dose Modification
Hematologic	Grade 4 thrombocytopenia, each occurrence	Withhold pomalidomide treatment and follow complete blood count weekly until thrombocytopenia improves to \leq Grade 2, then resume pomalidomide at 1 mg less than previous dose PO daily ^a .
	Grade 4 neutropenia or any grade febrile neutropenia, each occurrence	Withhold pomalidomide treatment and follow complete blood count weekly until neutropenia improves to \leq Grade 2, then resume pomalidomide at 1 mg less than previous dose PO daily ^a .
Gastrointestinal	Grade 1 or higher AST or ALT elevation, or elevation from baseline CTCAE grade	Withhold pomalidomide treatment until liver enzymes return to normal or baseline. Consider resuming pomalidomide at 1 mg less than previous dose ^a .
Other	\geq Grade 3 nonhematologic toxicity	Withhold pomalidomide treatment and follow for improvement of toxicity to \leq Grade 2, then resume pomalidomide at 1 mg less than previous dose PO daily. Permanently discontinue pomalidomide for angioedema, anaphylaxis, Grade 4 rash, skin exfoliation, bullae, or any other severe dermatologic reaction.

a If toxicities occur after dose reduction to 1 mg, discontinue pomalidomide.

ALT = alanine aminotransferase, AST = aspartate aminotransferase, CYP = cytochrome P, NCI-CTCAE = National Cancer Institute's Common Terminology Criteria for Adverse Events, PO = taken orally

If necessary to coadminister strong inhibitors of CYP1A2 in the presence of strong inhibitors of CYP3A4/5 and P-glycoprotein, consider reducing pomalidomide dose by 50%.

Dose modification guidance is based on pomalidomide prescribing information, which contains additional guidance on pomalidomide dosing.

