4.2 DLT Evaluatable (DE) Analysis Set

The DLT-evaluative (DE) analysis set will include all treated patients who either (1) experience a DLT, or (2) receive at least 75% of the intended SEA-BCMA dose and are followed for the full DLT evaluation period. The DLT evaluation period is defined as cycle 1 of treatment. For q2wk schedule, cycle 1 includes the first 2 doses of treatment. Patients will be replaced for DLT evaluation if they received prohibited medications (as described in protocol Sections 5.4.2 and 5.4.3), or are deemed inevaluable for clinical reasons by the SMC. Patients on the q2wk dosing schedule who receive only the 1st dose during cycle 1 for reasons other than toxicity may not be DLT-evaluative and will be replaced.

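### DLT evaluability in the combination run-ins sets a minimum SEA-BCMA dose but none for pomalidomide or dexamethasone, so a subject with little partner-drug exposure counts by default as DLT-free

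*Protocol*

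**What the plan says.** Three places define the DLT-evaluable set. The Protocol synopsis (Statistical Methods) admits treated subjects who had a DLT or who "were followed for the full DLT evaluation period and did not receive prohibited treatment"; it sets no minimum dose of any drug. Protocol Section 9.3.1.7.3 adds, for subjects without a DLT, that they "received a minimum 75% of the intended total Cycle 1 SEA-BCMA dose". SAP Section 4.2 asks that patients without a DLT "receive at least 75% of the intended SEA-BCMA dose and are followed for the full DLT evaluation period". None of the three mentions exposure to pomalidomide or dexamethasone.

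SAP 4.2 replaces patients who took prohibited medication "or are deemed inevaluable for clinical reasons by the SMC". It also replaces q2wk patients who missed the second Cycle 1 infusion for a reason other than toxicity.

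For Part D, Protocol Section 3.1.3.3 states: "The dose will be considered tolerable if ≤ 1 DLT is observed among the first 6 subjects". Section 3.1.3.2 applies the same limit to each Part C dose level before expansion. Both sections replace non-evaluable subjects, and neither gives its own definition of evaluable.

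A partner drug can stop while SEA-BCMA goes on. Protocol Section 4.4.1 says of Part D: "Subjects who discontinue pomalidomide may continue to receive SEA-BCMA and dexamethasone with medical monitor approval". It has matching provisions for dexamethasone in Parts C and D. Table 7 in Section 5.4.4 says, for an AST or ALT rise of Grade 1 or higher: "Withhold pomalidomide treatment until liver enzymes return to normal or baseline".

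**The concern.** The run-ins in Parts C and D are there to test combinations, but the exposure test for counting a subject refers to one drug of the two or three. A subject who leaves pomalidomide after a few days, receives both infusions and is followed through Cycle 1 fills one of the six places and enters the count as a triplet subject without a DLT. If pomalidomide adds toxicity, that subject had less chance of a combination DLT than a fully exposed one, and the limit of 1 in 6 becomes easier to meet.

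At stake is how a pass is read. In Part D, the tolerability statement on six subjects is the basis for any decision to amend and expand. In Part C, the same limit governs expansion to 20 per dose level. The reader of the results may not be able to see the problem: SAP 6.4 spells out intended dose intensity for SEA-BCMA schedules only, and SAP 5.1 confines DLT summaries to the dose-escalation part.

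**Working it through.** **Step 1. Can an under-exposed subject be evaluable?** Take Part D at 1600 mg on Days 1 and 15.

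- Intended Cycle 1 SEA-BCMA: 2 × 1600 = 3200 mg. The 75% threshold is 0.75 × 3200 = 2400 mg. Both infusions give 100% and pass; one gives 50% and fails.
- Intended pomalidomide: 21 daily doses. Suppose 3 are taken: 3/21 = 14.3%. No threshold applies.
- Intended dexamethasone: 4 doses. Suppose 1 is taken: 1/4 = 25%. No threshold applies.

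With full follow-up, no DLT and no prohibited treatment, this subject meets Protocol 9.3.1.7.3 and SAP 4.2 as written.

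**Step 2. Which early stops escape the DLT definition (Protocol 3.1.5)?** A stop caused by a qualifying event is already counted as a DLT, whatever the exposure. What remains is:

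- lower-grade toxicity, such as the Grade 1 AST or ALT rise in Table 7;
- Grade 4 neutropenia of 5 days or less, for which Table 7 withholds pomalidomide but which is not a DLT;
- stops unrelated to any adverse event;
- events judged clearly unrelated to SEA-BCMA.

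The delay criterion in 3.1.5 covers SEA-BCMA delays only, so a long pomalidomide hold is not itself a DLT.

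**Step 3. Illustrative size.** The documents give no pass probability for the 6-subject run-ins and no combination DLT rate, so there is no planned figure to reproduce and the rates below are assumptions. Let p1 be the DLT rate on the full triplet, p0 the rate when pomalidomide stops early, and m the number of under-exposed subjects among six. With independent subjects:

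P(pass) = [(1−p1)^(6−m) + (6−m)·p1·(1−p1)^(5−m)]·(1−p0)^m + (1−p1)^(6−m)·m·p0·(1−p0)^(m−1)

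For p1 = 35% and p0 = 10%:

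- m = 0: 0.65^6 + 6 × 0.35 × 0.65^5 = 0.0754 + 0.2437 = 0.319
- m = 1: (0.1160 + 0.3124) × 0.9 + 0.1160 × 0.1 = 0.3856 + 0.0116 = 0.397
- m = 2: (0.1785 + 0.3845) × 0.81 + 0.1785 × 0.18 = 0.4560 + 0.0321 = 0.488

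Other assumed rates:

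| p1 | p0 | m = 0 | m = 1 | m = 2 |
|---|---|---|---|---|
| 25% | 5% | 0.534 | 0.613 | 0.696 |
| 25% | 10% | 0.534 | 0.593 | 0.655 |
| 30% | 10% | 0.420 | 0.492 | 0.571 |
| 40% | 5% | 0.233 | 0.324 | 0.441 |
| 40% | 10% | 0.233 | 0.311 | 0.408 |

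Across these rows, one under-exposed subject adds about 6 to 9 percentage points to the chance of a pass, and two add about 12 to 21.

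**Step 4. Direction for dexamethasone.** Section 5.5 adds a corticosteroid premedication after an infusion reaction in subjects not receiving dexamethasone, and Section 3.1.5 makes any Grade 3 or higher infusion reaction in a premedicated subject a DLT. Losing dexamethasone could therefore raise DLT risk as well as lower it. The calculation above applies to pomalidomide only.

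**The case against.** The strongest reply is that the plan already leaves room to handle such a subject. SAP 4.2 gives the SMC an open power to declare a patient inevaluable, the SMC reviews run-in data (Protocol 3.1.9.2), and its detailed process sits in a separate document not available here. That stands, and it is why the subject counts by default rather than inevitably. But the power names no partner-drug criterion, and the clause is absent from Protocol 9.3.1.7.3.

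A pass also has limited automatic effect. Part D expansion needs data review and a protocol amendment, Part C expansion needs an SMC recommendation, and the study-wide stopping rules keep running. That stands too, though those reviews rest on the same six subjects.

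A reader might infer that the definition is a monotherapy rule never revisited for combinations. The documents do not support this. Section 9.3.1.7.3 refers to Section 5.6.2, which has a Part D exception on growth factor and transfusion support, and the Amendment 8 change summary lists 9.3.1.7.3 among the sections edited when Part E was removed.

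Finally, the frequency is unknown. Nothing in the documents says that one or two of six subjects would stop a partner drug early. The AST/ALT row in Table 7 is a hold after which resumption may be considered, and carrying on with SEA-BCMA after a partner drug is discontinued needs medical monitor approval.

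**Conclusion.** The gap is real in both documents. Followed as written, the rule lets a subject with little partner-drug exposure, full follow-up and both SEA-BCMA infusions count as DLT-free for the combination unless the SMC chooses otherwise. It matters most in Part D, where less pomalidomide would be expected to favour a finding of tolerability. In Part C the direction is uncertain, but such a subject still does not test the combination.

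The shift from 32% to 40% or 49% is an illustration. It rests on assumed DLT rates, assumed numbers of early stoppers and independence between subjects. Two stronger readings should be resisted. One is that both combination run-ins are shown to be biased toward passing; the dexamethasone reasoning does not support that. The other is that a partner-drug minimum would recover the whole difference. It would recover only the part due to non-toxicity stops, because subjects who stop for toxicity should stay in the set; the Grade 1 AST/ALT case is one of these. This is a cheap improvement worth making, not a flaw that invalidates the run-ins.

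**What to change.** In Protocol 9.3.1.7.3 and SAP 4.2, with the synopsis brought into line, require for Parts C and D that subjects without a DLT also received a minimum share of planned Cycle 1 doses of each partner drug. The sponsor sets the share. If it were the same 75%, it would mean 16 of 21 pomalidomide doses (0.75 × 21 = 15.75) and 3 of 4 dexamethasone doses.

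- Replace subjects below the minimum for reasons other than toxicity. SAP 4.2 already applies this principle to a missed second SEA-BCMA infusion.
- Keep subjects below it because of toxicity in the set, so that replacement does not depend on tolerability. Report their partner-drug exposure to the SMC and alongside the DLT count, so that a pass is not read as tolerability at full exposure.
- Extend the DLT reporting in SAP 5.1 and 6.6.2 to the run-ins, since it is now limited to dose escalation and the count would otherwise have no table.

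The cost is wording, an occasional replacement of a run-in subject (already permitted) and use of the pomalidomide dosing record, because most doses are self-administered. If the run-ins are already complete, the rule cannot be changed prospectively, but Cycle 1 partner-drug exposure can still be reported for each run-in subject.
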